8.3. Study Visits

Peanut OIT Treatment Overview

Peanut OIT administration will include an Initial Dose Escalation Day (IDED) with peanut oral immunotherapy dosing beginning at 0.5 mg with graduated doses up to 6 mg (if tolerated) occurring in the Stanford CFRU. Subjects tolerating less than 1.5 mg single dose will be considered an Initial Dose Escalation Day failure and will be discontinued from the study.

A targeted history and physical assessment will be performed at each in person visit. Physical assessments performed in this protocol will be allergy focused and include the following systems: head and neck, including thyroid; eyes, ears, nose, and throat; lungs; heart; abdomen; and skin. Subjects will be assessed for exacerbation of atopic dermatitis or asthma (as determined by active wheezing) prior to each in-CFRU dosing. In the presence of an exacerbation of atopic dermatitis, the study physician will use their professional judgment in deciding whether the exacerbation should preclude an attempt at updosing. In the presence of wheezing in any child, regardless of asthma history, spirometry (per manual of procedures) will be performed to assess FEV1. If FEV1<80% predicted value, bronchodilators will be administered and spirometry will be repeated. If FEV1 ≥80% predicted value (with or without bronchodilator administration) the updose will be attempted in CFRU. If FEV1 <80% predicted value after bronchodilator administration, the participant will remain at their current dose for two additional weeks. That day's dose may be administered either in CFRU and monitored as an updose.

In addition to dosing visits, subjects will return to the CFRU at designated visits (**see Appendix 1**) for their OFC or other assessments/blood draws. A medical and diary review, and targeted physical assessment will also be performed at these visits. OFCs will occur every 3 months (approximately every 13 weeks) beginning with week 104.

After subjects have met the criteria outlined above (Section 3.1), medical history, diet history, spirometry, SPT, and a physical assessment will be performed. These subjects will be randomized 1:1 either to avoid OIT therapy (**see Figure 1**), and begin the avoidance phase, or they will be randomized to decrease their daily dose to 300 mg of peanut protein. After 3 months both arms will be re-challenged with 4,000 mg peanut protein, and then every 13 weeks for up to 4 additional OFCs. The placebo group may be unblinded to the research staff at week 117.

Peanut OIT:

Initial Dose Escalation Day (Day 0) – The Initial Dose Escalation (IDE) Day will be done at the CFRU and consist of peanut OIT dosing, beginning at 0.5 mg of peanut protein with graduated doses every 30 minutes up to 6 mg (see schedule for initial day dose escalation, **Table 1**). Subjects will not have active wheezing, spirometry demonstrating FEV1 <80% predicted, or a current flare of atopic dermatitis that contraindicates dosing in the clinical judgment of the study physician. A physician will be present at all times during any of the CFRU peanut OIT dosing visits and will be available to respond within 60 seconds to any allergic reaction. Subjects tolerating the 6 mg single dose will remain on that daily dose for 2 weeks. They will then return every 2 weeks to the CFRU for single updose. Subjects who do not tolerate the 1.5 mg dose will be considered treatment failures and will not initiate home dosing.

Table 1: Peanut Protein or Placebo (oat protein)Dosage Escalation Schedule on the Initial Dose Escalation Day

Dose #	Peanut Dose	Cumulative Peanut Dose	
1	0.5 mg	0.5 mg	
2	0.8 mg	1.3 mg	
3	1.5 mg	2.8 mg	
4	3.0 mg	5.8 mg	

5 6.0 mg 11.8 mg

Up-dosing phase (build-up phase) (Week 1-44): Subjects will receive subsequent doses (**Table 2**) at home for the next 14 days. Subjects who tolerate only 1.5 mg on the IDED will return in 7 days for updosing to 3 mg and then return 7 days later for updosing to 6 mg before proceeding to dose #6. Subjects who tolerate only 3 mg on the IDED will return in 7 days for updosing to 6 mg before proceeding to dose #6. Subjects will be instructed to continue dietary peanut avoidance throughout the entire study. They will also be instructed not to introduce any new foods to the diet and to continue avoidance of the subject's other known food allergens, if any. At 2-week intervals, the subjects will return for a possible increase in the daily oral dose until they reach 4,000 mg peanut protein build-up phase).

During dose escalation, there should be increased hydration (i.e. about 16 oz or more given orally) and restricted exercise for 2 hours after dosing.

Dose #	Dose	Interval (Weeks)	% of Increase
5	6 mg	2	Initial Dose Escalation Day
6	12 mg	2	100%
7	25 mg	2	108%
8	50 mg	2	100%
9	75 mg	2	50%
10	100 mg	2	33%
11	125 mg	2	25%
12	156 mg	2	25%
13	195 mg	2	25%
14	245 mg	2	25%
15	306 mg	2	25%
16	383 mg	2	25%
17	479 mg	2	25%
18	599 mg	2	25%
19	749 mg	2	25%
20	936 mg	2	25%
21	1,170 mg	2	25%
22	1,463 mg	2	25%
23	1,829 mg	2	25%
24	2,286 mg	2	25%
25	2,858 mg	2	25%
26	3,573 mg	2	25%
27	4,000 mg	2	12%

Table 2: Dail	y Peanut Protein	Dosing and Increas	se Schedule for	Build-Up Phase
---------------	------------------	---------------------------	-----------------	----------------

Subjects will begin the CFRU dosing schedule as outlined above until 4,000 mg of peanut protein is reached. Any updosing attempts may be postponed for 1-2 extra visits based on clinical judgment. However, an updosing attempt must be made within a maximum of 3 consecutive scheduled clinic visits. Subjects should withhold their daily home dose and any prophylactic antihistamines on the in-CFRU updosing day but should take all other prescribed medications. Note that the daily home dose should be taken as part of a meal at a consistent time (within 24±2 hours of the previous day's dose), and it is critical to take the dose every day. Doses should be separated by at least 12 hours. Subjects who require dosing reduction during the 2-week period due to illness will undergo an attempted updosing only after resuming their full dose for a minimum 3 days.

As stated above, an updosing attempt must be made within 3 clinic visits on a given dose, unless updosing is delayed due to administration of epinephrine as defined in Section 7.4 or illness. If the subject fails to successfully increase updosing for three consecutive attempts, updosing will be halted at the last tolerated dose and the subject will continue on that dose as their maintenance dose for the remainder of the study. The subject will be followed for the remainder of the study for safety and immunologic monitoring.

Vigorous exercise is not permitted for at least 2 hours after the dose of oral allergen immunotherapy. Also, there must be at least 1 hour between vigorous exercise and taking a dose of oral allergen immunotherapy. Allergic reactions are still possible when exercise takes place more than 2 hours after the dose.

Should significant systemic symptoms, which may include mild symptoms based on physician discretion or moderate or greater symptoms, be reported during the daily home dosing, the symptom/dosing algorithm will be followed to determine the best course of action. The appropriate treatment will depend on the type and number of symptoms. Subjects will be allowed to take their other daily medications during the build-up and maintenance phases of the study (i.e., antihistamines, albuterol) except where prohibited in this protocol.

Every 13 weeks during the build-up phase, subjects will have blood drawn for mechanistic labs, including basophil activation studies and pregnancy testing, if applicable. Blood will be collected prior to attempted dose escalations, but the decision to updose will be made based on clinical parameters, not the results of the assays.

Weeks 52, 65, 78, and 91– Maintenance Phase

Subjects will undergo updosing until reaching a daily maintenance dose of 4,000 mg and they will remain at that dose and return for follow-up visits at Weeks 52, 65, 78, and 91. Each of these visits will include a physical assessment, spirometry, skin test, and blood draw for mechanistic studies. Based on our previous data using a similar dosing method (Table 2), we expect all subjects on active treatment to reach 4,000 mg between the Week 44 and Week 78 visits.

Week 104 - On Study DBPCFC (to 4,000 mg)

At Week 104 all subjects will have a DBPCFC to 4,000 mg (as per staged challenge above) to assess desensitization. The visit will also include a physical assessment, spirometry, skin prick test and blood draw for mechanistic studies.

The subject's sensitivity to peanut allergen is defined as the dose at which the subject experiences allergic reactions. All symptoms and signs will be evaluated and rated based on a standardized oral food challenge scoring system (Appendix 4).

During the oral food challenge, there should be increased hydration (i.e. about 16 oz or more orally).

Updosing during the DBPCFC will be stopped when the Principal Investigator (or designee) finds symptoms and/or signs that indicate a definite allergic reaction (Bock scoring system (objective, **Appendix 4**) has occurred based on clinically significant changes in reported symptoms, physical findings, or vital signs that the subject is experiencing to the challenge material. The challenge will consist of 7 doses (peanut or placebo), given about every 15-30 minutes for lower doses and about every 45 minutes or longer for higher doses (in bold): 5 mg, 50 mg, 220 mg, **625 mg, 1,000 mg, and 1,050 mg and 1,050 mg** (4,000 mg protein total). The doses for DBPCFCs conducted on or after Week 104 in this
protocol were selected with the rationale that some study subjects will be receiving placebo and would be expected to maintain the same level of sensitivity displayed at the screening DBPCFC to a cumulative dose of 500 mg of peanut protein. Both peanut and oat protein will be concealed in a food that masks the taste. After the last dose of the DBPCFC, the subject will be monitored for 2 hours and then discharged home. Subjects will be considered to have tolerated the OFC if they do not experience any objective reactions by Bock's Criteria (**Appendix 4**).

If the subject experiences reactions, they will be treated with the necessary rescue medications. They will be observed for a minimum two hours after the final administered dose and discharged home only when deemed clinically stable by a study physician.

After the Week 104 DBPCFC, subjects who meet the following criteria will reduce their daily maintenance dose to 300 mg peanut protein daily or to discontinue peanut protein daily dosing entirely (i.e., switch to 600mg oat flour):

- On OIT treatment for minimum 104 weeks,
- Taking daily maintenance dose of 4,000 mg protein for at least 3 months,
- No severe reactions (Bock's Criteria Grade 3, APPENDIX 4) to home dosing from Week 92-Week 104, and/or
- No objective reactions by Bock's Criteria, Appendix 4 at the DBPCFC at Week 104

Subjects who do not meet these criteria at Week 104 will be considered desensitization failures and will be offered a follow-up protocol that is separate from this protocol once they reach the primary endpoint. They will be considered in statistical analyses of the intent-to-treat population.

After Week 104, double blinding will continue by using the same quantity of flour for all groups (600 mg total of oat flour daily for placebo group and 600 mg total of oat flour daily for avoidance group; approximately 600 mg total of peanut flour --to provide exactly 300 mg peanut protein—for the 300 mg peanut protein group).

Separate GI Sub Study.

Subjects will undergo the second endoscopy at week 52, and a third endoscopy at week 104 and a fourth endoscopy at week 117 (or equivalent). These will be performed by a board certified gastroenterologist at Stanford Endoscopy suite. This will be performed under mild anesthesia using fentanyl, versed and midazolam and subjects will be observed in the endoscopy recovery room per standard of care. Biopsies will be taken from the esophagus, stomach and duodenum.

Weeks 117 (or equivalent), 130, 143, and 156 - On Study DBPCFC (to 4,000 mg)

At Weeks 117 (or equivalent), 130, 143, and 156, subjects will have a DBPCFC to 4,000 mg (as per staged challenge above) to assess tolerance. Subjects who fail these challenges (i.e., who exhibit objective reactions by Bock's Criteria, **Appendix 4**) will be offered a follow-up protocol that is separate from this protocol.

Subjects who are randomized either to 300 mg peanut protein or peanut avoidance or the placebo subjects who pass the week 104 criteria will return to CFRU at Weeks 117 (or equivalent), 130, 143, and 156. Each of these visits will include a physical assessment, spirometry, skin test, blood draw for mechanistic studies, and a DBPCFC to 4,000 mg as outlined above to assess clinical reactivity.

During the oral food challenge, there should be increased hydration (i.e. about 16 oz or more given orally).

There are no data indicating that repeating food challenges every 3 months will or will not induce desensitization or otherwise affect the outcomes in this study. Our preliminary studies in which we have performed DBPCFCs every 3 months in a separate phase 1 study cohort (n=87 subjects) have demonstrated no increased risk of sensitization.

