The PI will be available for questions and decision making for any questions related to the study protocol at all times.

All subjects will be observed for a minimum of 2 hours following administration of the final dose and will be discharged only when deemed clinically stable by a study physician.

Figure 3: Management of Symptoms During Initial Dose Escalation Day

Reactions to Peanut OIT During Build-up or Maintenance Phase

To be able to be eligible for an updosing or maintenance dose visit, subjects cannot have active wheezing, spirometry (as per manual of procedures) demonstrating FEV1 <80% predicted, or a current flare of atopic dermatitis that contraindicates updosing in the clinical judgment of the study physician. As needed, subjects will be maintained on their current dose of study product until their flare of asthma or atopic dermatitis is resolved.

If a subject has an updosing in the CFRU without symptoms, the action should be to continue per protocol with daily home dosing of the tolerated dose with the next updosing visit 2 weeks later.

If the subject only experiences oral/pharyngeal pruritus during the administration of the daily dose, then the same dose can be repeated the next day at home and continued throughout the interval unless other symptoms begin to develop.

For other mild symptoms (Objective, **APPENDIX 4**), the action should be either to repeat the dose the next day (day 2) at home or to have the subject return to the CFRU the next day (day 2) for a repeat of the previous day's dose or the last tolerated dose (at the study physician's discretion). If the dose is tolerated, then the subject will continue on that dose and return at the normal interval. If the dose causes mild symptoms again, then the subject may return to the CFRU the next day (day 3) and be given the last tolerated dose or a 1-2 step dose reduction. If tolerated, the subject will continue on this dose for the normal time interval. If mild symptoms recur, a 1-2 step reduction should be administered the next day (day 4). If tolerated then that dose should be continued for 2 weeks. If not tolerated, consultation with the PI is indicated.

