Any subject deemed to have severe allergic reactions to OIT, including hypoxia, hypotension or change in mental status and receives aggressive therapy (e.g., IV fluid resuscitation, mechanical ventilation, repeated doses of epinephrine for a life threatening reaction) at any time should be discussed with the PI and discontinued from active therapy.

For specific questions related to dosing escalation or continuation of the same dose that are not answered in the above protocol, the PI will be available for questions and decision-making.

Any subject who discontinues build-up dosing due to repeated allergic reactions to the characterized peanut allergen will have his/her blood drawn for mechanistic studies within approximately 1 week of discontinuation of therapy.

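### Section 8.3 directs an updose in a wheezing child once FEV1 is at least 80% predicted, although Section 6.4 makes active wheezing alone a bar to the updosing visit

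*Protocol*

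**What the plan says.** Two parts of the protocol decide whether a wheezing subject may have the dose raised.

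- **Section 6.4, build-up and maintenance reactions.** "To be able to be eligible for an updosing or maintenance dose visit, subjects cannot have active wheezing". The same sentence then lists FEV1 below 80% of predicted, and a flare of atopic dermatitis that the physician judges a contraindication. The next sentence gives the consequence: "As needed, subjects will be maintained on their current dose of study product until their flare of asthma or atopic dermatitis is resolved".
- **Section 8.3, treatment overview.** "Subjects will be assessed for exacerbation of atopic dermatitis or asthma (as determined by active wheezing) prior to each in-CFRU dosing". For wheeze it sets out a pathway: "In the presence of wheezing in any child, regardless of asthma history, spirometry (per manual of procedures) will be performed to assess FEV1". Then: "If FEV1<80% predicted value, bronchodilators will be administered and spirometry will be repeated". Then: "If FEV1 ≥80% predicted value (with or without bronchodilator administration) the updose will be attempted in CFRU". The dose is held for two more weeks only where FEV1 is still below 80% after a bronchodilator.

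Three other provisions bear on the point. For the Initial Dose Escalation Day, Section 8.3 uses the same form of words as 6.4: "Subjects will not have active wheezing, spirometry demonstrating FEV1 <80% predicted". In the up-dosing text, Section 8.3 allows an attempt to be put off by one or two visits on clinical judgment, with an exception for illness to the three-visit limit. Section 6.4 refers to the principal investigator matters described as follows: "For specific questions related to dosing escalation or continuation of the same dose that are not answered in the above protocol".

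**The concern.** Section 6.4 treats wheeze and low FEV1 as two independent reasons not to updose. Section 8.3 starts from a wheezing child and then decides on FEV1 alone. A child can wheeze and still blow 80% or more of predicted, and for that child one section bars the visit while the other directs the increase.

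What is at stake is dosing safety. This check comes immediately before an increase in allergen dose, and Section 8.3 itself uses active wheezing as its marker of an asthma exacerbation. Staff who follow the 8.3 pathway as written could raise the dose in a subject whom 6.4 makes ineligible. Section 15.1 permits no departures from the protocol, so following one section here would depart from the other.

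**Working it through.** No arithmetic applies and the plan has no figure to reproduce. The check is to run both rules on each kind of wheezing child who might present at a build-up visit.

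| Child at the visit | Section 6.4 | Section 8.3 pathway |
|---|---|---|
| Wheezing, first FEV1 at least 80% | Not eligible | Updose |
| Wheezing, FEV1 below 80%, then at least 80% after bronchodilator, wheeze still present | Not eligible | Updose |
| As above, but wheeze gone after bronchodilator | Wheeze bar no longer met; silent on whether the repeat FEV1 counts and whether the flare has resolved | Updose |
| Wheezing, FEV1 still below 80% after bronchodilator | Not eligible | Hold two weeks |

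The first two rows are a direct conflict. The third is a matter of detail that 8.3 can reasonably supply. The fourth agrees.

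Next, can the first two rows be reconciled from the text?

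1. *Does 8.3 merely elaborate 6.4?* If an FEV1 of 80% were enough, the separate mention of wheezing in 6.4 would do no work. The Initial Dose Escalation Day text also lists the two bars separately.
2. *Does 8.3 mean a different kind of wheeze?* No. Its pathway follows directly on the instruction to look for an exacerbation by active wheezing before each clinic dose.
3. *Does physician judgment in 6.4 cover wheeze?* The judgment clause most naturally attaches to the atopic dermatitis flare. Section 8.3 points the same way: it leaves dermatitis to professional judgment and then switches to a fixed FEV1 threshold for wheeze. Even if the clause covered all three items, the 8.3 threshold would still replace that judgment.
4. *Does the bronchodilator step guarantee that the wheeze clears?* No. It is mandated only below 80%, and what is repeated afterwards is spirometry. No branch asks for the chest to be listened to again.
5. *Does the referral to the principal investigator settle it?* It covers questions the protocol leaves unanswered. This one is answered twice.

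No text states which section takes precedence.

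**The case against.** The strongest reply is that staff are never compelled to breach anything. The up-dosing text lies in the same Section 8.3 and lets any attempt be postponed on clinical judgment, with an exception for illness. A clinician who holds the dose therefore satisfies both sections, and 6.4 indicates when to do so. On this view the 8.3 pathway is a default with a clinical override. Other safeguards stand too: lung examination at in-person visits, spirometry at every build-up visit (Appendix 1), and a physician present for clinic dosing.

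Most of this stands. A reader might infer that the protocol forces staff to updose a wheezing child, and it does not. But the permission to postpone is general and optional. It makes holding compliant without making the updose compliant with 6.4, and the specific instruction for wheeze still points to the increase.

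Some other inferences go further than the text allows:

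- *That a wheezing child with FEV1 of 80% or more is updosed untreated.* Section 8.3 requires a bronchodilator below 80% but does not forbid one above it.
- *That limiting the pathway to children leaves adults exposed.* Section 6.4 covers all subjects, so a wheezing adult is simply ineligible. The limitation is untidy, not unsafe.
- *That the silence of 6.4 on post-bronchodilator FEV1 is a second conflict.* Section 8.3 fills that silence.
- *That the Grade 1 wheeze entry in Appendix 4 shows added risk.* That scale grades reactions to dosing or challenge, not a sign found beforehand.

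**Conclusion.** The inconsistency is real and narrow. For a child with active wheezing and FEV1 at or above 80% of predicted, Section 6.4 bars the updosing visit and Section 8.3 directs the updose, with no rule of precedence. Holding is permitted but is not required by the 8.3 pathway.

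Its size cannot be put in numbers. The protocol does not say how often a child wheezes with preserved FEV1 at a build-up visit, so neither affected visits nor reactions can be counted. It has no bearing on the primary comparison, the power calculation or any endpoint definition.

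The conclusion rests on reading the wheezing bar in 6.4 as unconditional, which is the natural reading. If the physician-judgment clause were taken to cover wheeze as well, the conflict would be between judgment and a fixed threshold, and would still need resolving. Because the text governs a safety check before an allergen increase and the correction is cheap, it should be amended.

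**What to change.** Replace the updose rule in the Section 8.3 overview with wording to this effect:

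> Where FEV1 is 80% of predicted or higher, before or after a bronchodilator, and the subject is free of active wheezing and meets the other eligibility conditions of Section 6.4, the dose increase is attempted in the clinic. In every other case the subject stays on the present dose for a further two weeks and is then reassessed.

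Apply the pathway to any subject instead of any child, and add a cross-reference in each direction between 6.4 and 8.3.

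Two clinical questions should be left to the investigator: whether to give a bronchodilator when FEV1 is already 80% or more, and whether clearing of the wheeze on the same day after a bronchodilator counts as resolution of the flare in the sense of 6.4. The wording above does not need to prejudge either.

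The cost is protocol wording in two sections, any matching line in the manual of procedures, and a notice to staff. Some updoses will be delayed by two weeks. As an indication of that cost only, and not of the hazard: a subject on course for the maintenance dose at Week 44 and held once would reach it at 44 + 2 = Week 46, within the Week 44 to 78 range that Section 8.3 expects. Sample size, endpoints and analysis do not change.
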